11.2 PRODUCT COMPLAINT/DEVICE DEFICIENCY DEFINITION

A product complaint/device deficiency is defined (21 CFR 820.3(b) and ISO 14155) as any alleged deficiency related to the identity, quality, durability, reliability, safety, effectiveness, or performance of a device. This may include malfunctions, user error and inadequacies in labeling. Product complaints can pertain to any marketed AMO device being used in the study as well as the investigational device. The investigator is to assess whether the deficiency could have led to a serious adverse event without suitable action or intervention or under less fortunate circumstances.

11.3 ADVERSE EVENT AND COMPLAINT REPORTING REQUIREMENTS

All adverse events and any complaint encountered using any AMO product, regardless of severity and whether or not attributed to the study device(s), are to be reported to AMO and submitted on the case report form corresponding to the visit during which awareness of the event occurred. Adverse events are also to be reported to the reviewing IRB as per the IRB's reporting requirements. If required, adverse events will be reported to the appropriate regulatory agencies (e.g., FDA) according to all applicable laws and regulations. Specific instructions on notification procedures to AMO are included in **Appendix E**, Adverse Event Reporting.

Reporting of adverse events shall follow the USA Code of Federal Regulations (21CFR812).

General guidelines are provided below:

Adverse Event Reporting

An adverse event that is not serious or device-related is to be reported to AMO in a timely manner. Notification of non-serious and non-device-related adverse events will occur by submitting events on the CRF when noted. Such adverse events are also to be reported to the reviewing IRB per their reporting requirements.

Complaints/Device Deficiency Reporting

A general product complaint or device deficiency is to be reported to AMO in a timely manner. Notification of complaints/device deficiencies will occur by either submitting complaints on the CRF when the complaint occurred (e.g., operative form) or by a phone call to the Sponsor. Any device deficiency that could have led to a serious adverse event without suitable action or intervention, or under less fortunate circumstances, must be reported to the sponsor immediately (no later than 48 hours after detection). Device deficiencies that could have led to a serious adverse event should also be reported to the investigator's IRB per their reporting requirements.

Serious and/or Device-Related Adverse Event Reporting

Serious and/or device-related events (ADEs) are to be documented using the SAE/ADE Detailed Page . In the event of a serious adverse event (SAE), which may or may not be related to use of the study device, AMO must be notified immediately (no later than 48 hours after detection). Any SAE is to be reported by phone (and/or email) and by submitting a completed SAE/ADE Detailed Page. Any SAE or device-related AE should also be reported to the investigator's IRB per their reporting requirements.

Unanticipated Adverse Device Effect (UADE)/Unanticipated Serious Adverse Device Effect (USADE) Reporting

If during the study, a serious adverse event occurs that may reasonably be regarded as device-related and was not previously expected in nature, severity, or degree of incidence, the investigator is to report the UADE/USADE to AMO within 48 hours, and to the investigator's IRB as soon as possible (and no later than 10 working days after learning of the event for sites in the USA as required by 21CFR812).

11.4 CAUSAL RELATIONSHIP

The investigator should always be alert to adverse events that may be related to the study device or the use of the study device (i.e., the procedure specific to the initial application of the device). An attempt should be made in every case to determine the causality of the event. The following definitions are to be used as guidelines in determining the relationship between the event and the study device and/or use of the device.

Definitely related:	If the event is associated with the device and/or the use of the device beyond a reasonable doubt, a causal relationship exists between the adverse event and the device and/or the use of the study device.
Probably related:	There is a reasonable possibility of a causal relationship between the adverse event and the device and/or the use of the study device and/or the adverse event cannot be reasonably explained by another cause.
Possibly related:	The adverse event has not been determined to be related to the device or the use of the device, but no other cause has been identified and the device and/or the use of the study device cannot be ruled out as a possible cause.
Unlikely to be related:	The possibility of a potential causal relationship between adverse event and the device and/or the use of the device could exist, but the adverse event can be reasonably explained by another cause.
Not related:	There is no possibility of a causal relationship between the adverse event and the device and/or the use of the study device and/or the adverse event can be attributed to another cause.

If an adverse event is believed to be definitely, probably or possibly related to the study device and/or the use of the device, the event will be considered related to the study device and/or the use of the device.

11.5 ADVERSE EVENT FOLLOW-UP

For every adverse event, appropriate measures should be undertaken to treat and/or monitor the subject until resolution occurs. Obtain and maintain in the subject's files all pertinent medical data relating to the event including the subject's medical records and medical reports and/or judgments from colleagues or outside specialists who assisted in the treatment and follow-up of the subject. The investigator should keep AMO closely informed as to the outcome of serious and/or device-related adverse events, thereby allowing AMO to comply with the appropriate regulatory reporting requirements. A SAE/ADE Resolution Form should be submitted each time the subject returns to the investigator or other specialist(s) for follow-up of a serious and/or device-related adverse event until resolution of the event. Any subject who is exited from the study due to a serious and/or device-related adverse event will be followed until the outcome is determined.

12. PROTOCOL CHANGES/AMENDMENTS

If the investigator desires to modify any procedure and/or the design of the study, he or she must contact and obtain consent from AMO regarding the proposed changes prior to

implementation. Any modifications (including additional data collection) require approval by the FDA as well as approval of the governing IRBs prior to implementation.

13. ETHICS REVIEW AND PATIENT WELFARE

13.1 INSTITUTIONAL REVIEW BOARD (IRB)

It is the responsibility of the investigator to obtain prospective approval of the study protocol, protocol amendments or changes, informed consent forms and other relevant documents (e.g., advertisements) from the IRB. All correspondence with the IRB should be retained at the site. Copies of IRB submissions and approvals should be forwarded to AMO.

The investigator is responsible for notifying the IRB of reportable adverse events as well as any other circumstance in which additional procedures outside the protocol were conducted to eliminate apparent hazards to subjects.

13.2 INFORMED CONSENT

The current version of the IRB-approved study informed consent must be signed by each study subject prior to any study-specific examinations being performed. The IRB-approved informed consent is to be signed and dated by the subject as well as by the person who conducted the informed consent discussion. The signed informed consent will be maintained by the investigator as a permanent part of the subject's medical records. A copy of the signed and dated form is to be provided to the subject. The investigator will provide AMO written acknowledgement on the preoperative case report form that a signed agreement of informed consent has been obtained and is in the investigator's possession for each subject. As required by 21CFR812 Part G, the site shall document in the source documents that informed consent was obtained prior to participation in the study for each subject enrolled.

NOTE: The informed consent process also includes obtaining the subject's signature on an Authorization for Use/Disclosure of Health Information for Research Form.

NOTE: The sponsor will secure appropriate insurance for study subjects prior to study start.

14. DOCUMENTATION

14.1 SOURCE DOCUMENTS

Source documents must be kept for all study subjects. Source documents may include a subject's medical records, hospital charts, clinic charts, the investigator's subject study files, as well as results of any diagnostic tests or procedures such as topographies or laboratory tests with photographs or instrument printouts.

Each site is expected to adhere to the clinic's own standard documentation requirements for medical charts/clinic notes. However, for the purposes of this clinical study, the medical charts/clinic notes must also include, at a minimum, the following data that will be considered source data and will be reviewed by AMO:

- Subject's name and study identification number
- Subject's contact information.
- Study protocol number and the Sponsor name (AMO)A statement that informed consent was obtained prior to participation in the study (including the date)
- Dates of all subject visits and surgeries throughout the duration of the study
- Implant serial number identification
- Concurrent medications
- Corrected and uncorrected distance visual acuity
- IOP
- ECC
- Manifest refraction
- Occurrence and status of any operative complications, postoperative medical findings and adverse events
- Occurrence and status of any subject complaints, e.g., ocular/visual symptoms
- The date the subject exited the study, and a notation as to whether the subject completed the study or reason for early exit.

14.2 SUBJECT CONFIDENTIALITY

Subjects will be assigned a site/subject number to maintain subject confidentiality. Subject names may possibly be disclosed to AMO or regulatory agencies during inspection of medical records related to the study, but reasonable precautions will be taken to maintain confidentiality of personal information to the extent permitted by applicable laws and regulations.

14.3 CASE REPORT FORM COMPLETION

This study will use an electronic data capture system. All study staff responsible for entering data into the system must complete certification prior to using the system. The investigator is responsible for ensuring that data are properly recorded on each subject's case report forms and related documents. Prior to database closure, the investigator will verify completeness and accuracy of all data collected.

14.4 STUDY SUMMARY

A final investigator's summary will be provided to AMO and the reviewing IRB within 3 months after termination or the completion of the study or the investigator's part of the investigation.

15. MONITORING

AMO will perform three types of monitoring to ensure compliance with regulations: data monitoring, administrative monitoring, and safety monitoring.

15.1 DATA MONITORING

In order to ensure a well-controlled clinical trial, AMO will follow specific data monitoring procedures. As this study is masked, any necessary review of safety and effectiveness data by OVD type will be done only by the Data Safety Monitoring Board (Section 15.3) until the final study visits are completed. Study staff and AMO personnel will remain masked until the final study visits have been completed.

An electronic data capture system (EDC) will be used to transmit case report forms from the investigative site to AMO. Requests for data clarification will be handled through this same system.

To minimize data omissions and inconsistencies on clinical reports and to ensure that data are accurately transcribed to computer data files, AMO will follow internal data processing procedures that include automated and manual quality control checks to identify any data discrepancies. Any such items will be resolved and documented as needed on the case report forms at the investigative site and in the data management system at AMO.

Prevention of Missing Data

Methods used to safeguard against missing data that can have deleterious effects on the study integrity and reliability of its outcomes will include training study staff with WebEx and on-site programs. In addition, subjects will be encouraged at the time of informed consent to avoid missing study visits, as missing data may affect the study reliability and diminish the scientific value of their contribution to the study.

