Inclusion and exclusion qualifications will be assessed at the preoperative visit according to the inclusion/exclusion criteria. The Informed Consent Document and Authorization for Use/Disclosure of Health Information form (HIPAA authorization) must be signed by

any patients who agree to participate in the study prior to undergoing any study-specific procedures. After determination that all inclusion/exclusion criteria have been met, enrolled subjects will be randomized in a 1:1 ratio. Subjects will receive the study OVD in one eye and the currently-available control OVD in the fellow eye. Subjects and study personnel will be masked for the duration of the study.

Key preoperative data include ocular health and history, visual acuities, manifest refraction, IOP, ECC, biomicroscopic slit-lamp findings, ocular symptoms and biometry. The operative visit will include standard procedures for cataract surgery and IOL implantation. All aspects of laser cataract surgery will be allowed as well as astigmatic keratotomy (AK) and Limbal Relaxing Incisions (LRI). If laser cataract surgery, AK or LRI is elected, it must be performed on both eyes of the subject.

A standardized medication regimen will be used preoperatively and intraoperatively (Section 10.5, Medication Regimen). Key postoperative data collection includes IOP, ECC, manifest refraction, visual acuity, visual symptoms, biomicroscopic slit-lamp findings, and adverse events.

As this study is masked, an independent Data Safety Monitoring Board (DSMB) will monitor adverse events that occur during the study.

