15.3 SAFETY MONITORING

This study will use a Data Safety Monitoring Board (DSMB) for safety monitoring. In alignment with ISO 14155:2011(E), the DSMB is an independent committee that is established by AMO to assess, at intervals, the progress of the clinical investigation, the safety data, or the critical performance endpoints, and to recommend to the sponsor whether to continue, suspend, or stop the clinical investigation. The DSMB will have access to the randomization code to be able to assess safety by OVD group if required. The responsibilities of the DSMB will be detailed in a separate written procedure to establish the frequency of meetings, handling of emergency situations and documentation of such meetings.

This study will also utilize a Medical Monitor for safety monitoring. The Medical Monitor will remain masked until the final study visits have been completed. The Medical

Monitor will review and assess any reports of serious and/or device-related adverse events as well as device deficiencies that could have led to a serious adverse event. If necessary, the medical monitor will discuss these events with the reporting investigator(s), without being specific about OVD type. If unmasking is required by the Medical Monitor to protect the safety of the subject(s), a request will be submitted and approved by Head of Clinical Research and Head of Biostatistics prior to release of the randomization code for only the subject(s) involved, and the IRB will be notified. The medical monitor will also be available to answer all questions from investigators. The medical monitor, as well as any other qualified personnel designated by AMO, shall also review interim progress reports, as applicable.

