20.4 INTERIM REPORTS

Due to the short duration of this study, no interim study reports are anticipated. However, should a progress report be required for regulatory purposes (e.g., FDA progress report), all masking will be maintained. If any interim analyses need be performed for product registration or release in other countries that require unmasking and reporting of effectiveness outcomes, they will be conducted by an independent body to avoid bias. Interim reports will not be disseminated to investigators/site personnel or to AMO staff working directly with study sites and monitoring incoming data.

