SAFETY (SF) ANALYSIS

The safety population will consist of all subjects who had any study OVD used and with data available at the time of analysis (i.e., no data imputation). For endpoint analyses using the safety population, if a subject receives only one study OVD then their data will be reported separately since they will not have any between eye difference values. However, if only one eye had a study OVD, then data for that eye will be included in reporting of adverse events and complications. Reporting of cumulative complications (occurring at any time postoperative) will include data from all eyes that had a study OVD.

PER-PROTOCOL (PP) ANALYSIS

The PP population will only include subjects who had surgeries with paired OVDs used, were evaluated within the proper study interval and were without clinically-relevant protocol deviations (deviations that could potentially impact the primary or secondary endpoints for either eye as determined prior to database lock). PP tables will include available data at the time of analysis with no data imputation performed.

Appendix I lists the analysis tables including the endpoints and the populations used to report the results.

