2.3 DATA CONVENTIONS

Descriptive statistics will typically include sample size (N), mean, standard deviation (SD), median, minimum (Min.), and maximum (Max.) as appropriate for continuous variables. For categorical data, the frequency and proportion will be computed.

For continuous variables, statistical tests assuming normality will generally be used. However the data will be reviewed to evaluate whether the normality assumption is appropriate. If it is found not to be appropriate, either an appropriate transformation of the data (i.e., logarithmic) may be used or the corresponding non-parametric tests may be used. Deviations from the proposed statistical guidelines will be substantiated by sound statistical rationale. In this study, unless otherwise indicated, paired t-tests will be used for continuous data, Wilcoxon signed-rank test for ordinal data and McNemar's test for dichotomous data.

Unless otherwise indicated, alpha will be set to 0.05 for two-sided statistical testing with alpha set to 0.025 for one-sided testing.

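### Masking is guaranteed only to the final study visits, not to database lock, so data verification, query resolution and per-protocol exclusions may be done with the OVD codes known

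*Protocol*

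**What the plan says.** **Where masking ends.** The protocol synopsis says in general terms that "Subjects and study personnel will be masked for the duration of the study". Section 15.1 is more specific: "Study staff and AMO personnel will remain masked until the final study visits have been completed". Until then, "review of safety and effectiveness data by OVD type will be done only by the Data Safety Monitoring Board". Section 15.3 repeats the trigger: "The Medical Monitor will remain masked until the final study visits have been completed". Section 10.8 has subjects told which product each eye received once they complete the study or leave it early, with no reference to lock.

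**What is still open after that point.**
- Protocol 14.3: "Prior to database closure, the investigator will verify completeness and accuracy of all data collected".
- Protocol 15.1: data discrepancies are resolved on the case report forms at the site and in the sponsor's data system.
- Protocol 15.2: a close-out visit to each site after study completion covers the last subject records.
- SAP 2.1: the per-protocol set leaves out subjects with clinically relevant deviations, meaning "deviations that could potentially impact the primary or secondary endpoints for either eye as determined prior to database lock".
- SAP 2.3: the data are reviewed for normality, after which "either an appropriate transformation of the data (i.e., logarithmic) may be used or the corresponding non-parametric tests may be used". For the primary ECC endpoint, SAP 5.2 provides only for a non-parametric test. Neither section makes masking a condition of the review.

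**Interim reports.** Protocol 20.4 anticipates none. If unmasked analyses were needed for registration or release in other countries, an independent body would do them, and "Interim reports will not be disseminated to investigators/site personnel or to AMO staff working directly with study sites and monitoring incoming data".

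**The concern.** The usual safeguard is that nobody who can still alter the data or the analysis sets knows the allocation until the database is locked. Here the guarantee stops one step earlier. The SAP mentions database lock once, in the per-protocol definition, and does not link it to unmasking.

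The paired-eye design sharpens this, because one eye's code gives away the other. Someone holding the codes could pick out the pairs in which only the test eye spiked while deviations were still being classified and IOP entries still queried. Two kinds of decision are exposed:

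- per-protocol exclusions, which affect the supportive analysis;
- late corrections to recorded readings, which carry into every population, including ITT.

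The wording on subject disclosure adds a second route. If the final study visits in 15.1 means those of the last subject, telling a subject the allocation at early exit comes before masking is due to end, and the site may learn it while that subject's records are still open.

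**Working it through.** The plan gives no figure on this point, so the first check sets the passages side by side. The second is an illustration of size.

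**1. Timing**

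| Activity | Deadline in the plan | Required to be masked? |
|---|---|---|
| Masking of site staff, sponsor personnel and Medical Monitor | Final study visits completed (15.1, 15.3) | Guarantee ends here |
| Query resolution | None stated (15.1) | Not stated |
| Close-out monitoring | After study completion (15.2) | Not stated |
| Investigator verification | Before database closure (14.3) | Not stated |
| Per-protocol exclusions | Before database lock (SAP 2.1) | Not stated |
| ECC normality review and test choice | None stated (SAP 2.3, 5.2) | Not stated |
| Telling subjects their allocation | After completion or early exit (10.8) | Not linked to lock |

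Every activity after the first row may therefore be carried out with codes known without breaching the text.

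**2. How few changes matter near the margin**

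Inputs: n = 200 evaluable subjects (SAP 1); spike rate 30% and correlation 0.5 (SAP 8); margin -10% on control minus test, one-sided alpha 0.025 (SAP 5.1). I use the paired Wald interval as a stand-in for the planned GLIMMIX analysis.

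Discordant share at equal rates: 2 × 0.30 × 0.70 × (1 - 0.5) = 0.21, so 0.21 × 200 = 42 pairs. I hold this total fixed and vary the split.

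With b test-only and c control-only pairs, d = (c - b)/n and

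lower bound = d - 1.96 × √{[(b + c)/n - d²]/n}.

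- **b = 25, c = 17, n = 200:** d = -0.040; SE = √[(0.21 - 0.0016)/200] = 0.0323; bound = -0.040 - 0.0633 = **-10.3%**, fails.
- **One test-only pair excluded (24, 17, n = 199):** d = -0.0352; SE = 0.0321; bound = **-9.8%**, passes. This is the per-protocol route.
- **One test eye changed from spike to no spike (24, 17, n = 200):** d = -0.035; SE = 0.0319; bound = **-9.8%**, passes. This route reaches ITT. It requires that the changed reading was the eye's only spike, because the endpoint is cumulative.

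Further from the margin more is needed:

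| Test-only / control-only | d | Lower bound | Exclusions needed to pass |
|---|---|---|---|
| 21 / 21 | 0.0% | -6.4% | 0 |
| 24 / 18 | -3.0% | -9.3% | 0 |
| 25 / 17 | -4.0% | -10.3% | 1 |
| 27 / 15 | -6.0% | -12.3% | 5 |
| 30 / 12 | -9.0% | -15.2% | 11 |

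A 25 / 17 split is not remote even if the products are equal: 0.040/0.0324 is about 1.2 standard errors below zero.

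**3. ECC test choice**

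In a simulation of 40,000 runs at the ECC margin with n = 195 pairs, freely taking the better of the paired t-test and the signed-rank test raised one-sided type I error from about 0.025 to 0.030 for normal differences and 0.033 for t-distributed differences with 4 degrees of freedom. This is an upper illustration, since it assumes an unrestricted choice.

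**The case against.** The other side has good points, and most of them stand as limits on the size of the problem.

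- **Until sets a minimum.** A reader might infer that the codes are released at the last visit. The documents do not say so; they only fail to forbid it.
- **Per-protocol exclusions do not decide the trial.** ITT is primary (Protocol 20.1, SAP 2.1), and the per-protocol analysis has no separate success criterion. The exclusions must also be settled before lock. What is missing is the word masked.
- **ECC reading is protected.** It is tempting to add late 3-month images to the list of exposed steps. Protocol Appendix C sends images to a central reading center without the treatment group, so unmasking site or sponsor staff does not by itself unmask the readers.
- **There is no re-adjudication step for spikes.** A spike is a Goldmann reading of at least 30 mmHg taken at a visit, with its own SAE/ADE page (Protocol 10.7) and source verification (15.2). Most such records are made while staff are masked. Only late corrections remain exposed.
- **The primary ECC rule is narrower than the general convention.** The transformation option stands in SAP 2.3; SAP 5.2 offers only a non-parametric test. The inflation from free choice is modest, and masking to lock would not by itself remove it, because a test is normally chosen at analysis.
- **Sections 20.4 and 15.1 do not flatly contradict each other.** The circulation limit in 20.4 is narrower than the masking in 15.1, because sponsor staff outside the two named groups are not mentioned. That they would see results is an inference from silence, about an analysis that is not anticipated.

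None of this closes the interval between final visits and lock, and no passage requires the work done in it to be masked.

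**Conclusion.** The gap is real and should be closed, but it is a moderate weakness and not a fatal one. The plan permits verification, queries, close-out monitoring and per-protocol exclusions to be done unmasked; it does not show that they will be, and it gives no count of decisions left open after the last visit.

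The size depends on how close the result falls to the margin. Under the assumptions above, one pair or one reading can reverse the conclusion at a 25 / 17 split, five exclusions are needed at 27 / 15, and none of it matters at equal observed rates. The illustration rests on 200 pairs, 42 discordant pairs held fixed, and a Wald interval. The documents do not support the stronger inference that the primary ITT result is open to selective exclusion: exclusions touch only the per-protocol analysis, and ITT is exposed only through changed data.

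**What to change.** 1. **Protocol 15.1 and 15.3:** make database lock, instead of completion of the final study visits, the point to which site staff, sponsor personnel and the Medical Monitor stay masked.
2. **Protocol 10.8:** defer telling subjects their allocation to the same point, including those who exit early.
3. **SAP 2.1:** require per-protocol exclusions to be decided and documented on masked data, before lock and before unmasking.
4. **SAP 2.3 and 5.2:** make the ECC normality assessment and the choice of test on masked data before unmasking. Naming the normality criterion and the alternative test in advance would strengthen this.
5. **Protocol 20.4:** align the circulation of any unmasked interim report with 15.1, so that sponsor personnel involved in the trial stay masked until lock.

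The cost is protocol and SAP wording. Sites, sponsor staff and subjects learn the codes a few weeks later.
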